I will provide all study personnel under my supervision copies of the protocol and access to all information provided by SynCore Biotechnology. I will discuss this material with them to ensure that they are fully informed about the drugs and the study.

I will conduct the trial in accordance with the guidelines of Good Clinical Practice (GCP) including the archiving of essential documents, the Declaration of Helsinki, any applicable local health authority, and Institutional Review Board (IRB) requirements.

Investigator Name (Printed)

Institution

Signature

Date

Please retain the original for your study files.

PROTOCOL SYNOPSIS

Name of Sponsor/Company: SynCore Biotechnology Co. Ltd.	
Name of Study Product: SCB01A	
Protocol Number: SCB01A-22	Indication: Recurrent or metastatic squamous cell carcinoma of head and neck
Title of Study: An open-label, phase II study to evaluate the efficacy and safety of SCB01A in subjects with recurrent or metastatic squamous cell head and neck cancer who have failed platinum-based treatment	
Study Center(s): Up to 4 centers in Taiwan	Study Development Phase: Phase II
Planned Number of Subjects: Up to 37 subjects will be enrolled, consisting of 10-13 subjects in Stage I and 19-24 subjects in Stage II, with replacement for those non-per protocol (non-PP) subjects (estimated 20% dropout rate).	

Study Rationale:
 
From pre-clinical pharmacology and phase I clinical study SCB01A has demonstrated promising anticancer action with a vascular disrupting activity that has the potential for treatment of various malignancies, particularly for patients with drug resistance. The drug has been studied in human subjects in a dose-escalation phase I study and has shown to be safe for up to 2 cycles of 24 mg/m² (each cycle consisting of one intravenous [i.v.] administration of SCB01A via a central line every 3 weeks). In the phase I study, partial response (PR) (shrinkage of tumor size to 50%) was observed in cycle 9 (3 mg/m²) of one subject with right buccal squamous cell carcinoma and 19/33 (58%) subjects had stable disease (SD) for more than 2 cycles.
 
Pre-clinical study of SCB01A showed that the concentrations at which tubulin inhibition occurred were around 80 nM for 24-hour exposure or 200 nM for 6-hour exposure. However, pharmacokinetic (PK) results of phase I study showed that the average elimination half-life (t_{1/2}) of a 3-hours i.v. infusion of SCB01A is approximately 2.5 hours and almost no SCB01A can be detected after 10 hours, indicating most subjects were treated in short API exposure time and may have been insufficient to achieve efficacy. Therefore, to extend the exposure duration above effective concentration in blood may increase the treatment efficacy.
 
The aim of this study is to evaluate the efficacy and safety of i.v. infusion for 24-hour of SCB01A in subjects with squamous cell carcinoma of head and neck who have failed previous platinum based therapies.
	

Objectives:
 
This is a Phase II study with intra-subject dose escalation to evaluate the efficacy and safety of SCB01A in subjects with recurrent or metastatic squamous cell carcinoma in head and neck.
 
Primary Objective:
 
To assess the objective response rate (ORR) during treatment phase according to the Response
	

Name of Sponsor/Company:

SynCore Biotechnology Co. Ltd.

Name of Study Product:

SCB01A

Protocol Number:

SCB01A-22

Indication:

Recurrent or metastatic squamous cell carcinoma of head and neck

Evaluation Criteria in Solid Tumors (RECIST) version 1.1.

Secondary Objective:

[figure not shown]
- To evaluate the safety and toxicity profile of SCB01A.
- To assess the overall survival (OS) after first treatment with SCB01A.
- To assess the progression-free survival (PFS).
- To assess the best overall tumor response after treatment with SCB01A.
- To assess the PK profile.

Trial Design:

Multicenter, open-label, phase II study of SCB01A administered to subjects with recurrent or metastatic squamous cell carcinoma of head and neck.

Intra-Subject Dose Escalation

All subjects enrolled in this study will be treated from the same starting dose 12 mg/m² (Dose 1) given on Days 1 and 8 in a 21-day cycle by 24 h IV infusion. If the subject experiences no dose-limiting toxicity (DLT) during the period, dose escalation of SCB01A to 18 mg/m² (Dose 2) occurred from Cycle 2; and increased to 24 mg/m² (Dose 3) on Cycle 3 ([Figure 1](#)).

Figure 1: Intra-Subject Dose Escalation**Dose modification**

If the subject experiences a DLT at a given dose level, dose escalation will be halted and a reduced dose will be given to the subject. Dose adjustments were allowed based on the toxicity, efficacy evaluation, and clinical judgement by physician.

[figure not shown]
Rules for dose modifications of the study ([Figure 2](#)) are listed as following:

1. Dose 1 (12 mg/m²), will be the starting dose regimen for all subjects. Safety and clinical benefit observation will be performed prior to drug administration on Cycle 2 Day 1.
 - a) Dose de-escalation: if any DLT experienced before Cycle 1 Day 8, the dose will be de-escalated to Dose 1a (9 mg/m²) for Cycle 1 Day 8. If first DLT during Cycle 1 is experienced after Cycle 1 Day 8, the dose will be de-escalated to Dose 1a (9 mg/m²) for Cycle 2. If no DLT is observed in Dose 1a, the subjects will receive the Dose 1a until PD, consent withdraw or death. Once more dose de-escalation (Dose 1b, 7 mg/m²) will be allowed if another DLT is observed in Dose 1a.
 - b) Dose maintained: If clinical benefit observed at Dose 1 and without DLT, the dose level can be maintained until PD, intolerable toxicity, consent withdraw or death.
2. Dose 2 (18 mg/m²), will be administrated for one cycle and safety and clinical benefit observation will be performed prior to drug administration on Cycle 3 Day 1.

Name of Sponsor/Company: SynCore Biotechnology Co. Ltd.	
Name of Study Product: SCB01A	
Protocol Number: SCB01A-22	Indication: Recurrent or metastatic squamous cell carcinoma of head and neck

- a) Dose de-escalation: if any DLT experienced before Cycle 2 Day 8, the dose will be de-escalated to Dose 2a (15 mg/m²) for Cycle 2 Day 8. If first DLT during Cycle 2 is experienced after Cycle 2 Day 8, the dose will be de-escalated to Dose 2a (15 mg/m²) for Cycle 3. If no DLT is observed in Dose 2a, the subjects will receive the Dose 2a until PD, consent withdraw or death. Once more dose de-escalation (Dose 2b, 12 mg/m²) will be allowed if another DLT is observed in Dose 2a.
- b) Dose maintained: If clinical benefit observed at Dose 2 and without DLT, the Dose 2 can be continued until PD, intolerable toxicity, consent withdraw or death.
- 3. Dose 3 (24 mg/m²), will be administrated for one cycle and safety and tumor assessment will be performed prior to drug administration on Cycle 4 Day 1.
 - a) Dose de-escalation: if any DLT experienced before Cycle 3 Day 8, the dose will be de-escalated to Dose 3a (20 mg/m²) for Cycle 3 Day 8. If first DLT during Cycle 3 is experienced after Cycle 3 Day 8, the dose will be de-escalated to Dose 3a (20 mg/m²) for Cycle 3. If no DLT is observed in Dose 3a, the subjects will receive the Dose 3a until PD, consent withdraw or death. Once more dose de-escalation (Dose 3b, 16 mg/m²) will be allowed if another DLT is observed in Dose 3a.

Figure 2: Dose Modification

If the subject experienced any neurotoxic DLT, the subject will be withdrawn.

Per-protocol (PP) subjects will be considered to be evaluable for ORR conclusion; Non-evaluable subjects will be replaced.

Simon’s Two-Stage Design¹

Stage I: A total of up to 10 evaluable subjects will be enrolled for Stage I to receive at least 3 cycles of i.v. administration by 24-hours infusion of SCB01A. The tumor response review will be

Name of Sponsor/Company: SynCore Biotechnology Co. Ltd.	
Name of Study Product: SCB01A	
Protocol Number: SCB01A-22	Indication: Recurrent or metastatic squamous cell carcinoma of head and neck

performed with the subjects who completed 3 cycles of SCB01A treatment. If at least one response (CR or PR) is observed, another 19 evaluable subjects will be enrolled into Stage II.
 
Stage II: 19 evaluable subjects will be enrolled at stage II and treated with the same intra-subject dose escalation regimen from starting dose 12 mg/m². The tumor response review will be performed with the subjects who completed 3 cycles of SCB01A treatment.
 
All subjects will be treated until the occurrence of progressive disease, intolerable adverse events (AEs)/toxicity, consent withdrawal or death. After discontinuation of study treatment, all subjects will be followed for survival and disease-specific therapies of the clinician's choice will be administered. Follow-up visits will be scheduled every 3 weeks for 9 weeks (i.e. week 3, week 6, and week 9), thereafter every 9 weeks until the end of the study (either 12 months after the 1st treatment with SCB01A or end of 27 weeks survival follow-up, whichever comes later).
 
Data and Safety Monitoring Board (DSMB)
 
The DSMB, composed of medical monitors (physicians experienced in oncology studies) and at least one statistician, Their responsibilities are to review and evaluate the data for safety, study conduct and progress, and make recommendations concerning the continuation, modification, or termination of study. Serial assessments of PK results also may be taken into account for safety evaluation. A neurologist will be invited to join DSMB meeting as a consultant when neurotoxicity occurred.
 
The document review or meeting of DSMB will be held when the following scenarios:
 
 • A subject is not recovered from Grade 2 neurotoxicity over three weeks; • A subject revealed Grade 3 or above neurotoxicity; • After 10 evaluable subjects finished the study in Stage I 	

Duration of Treatment:
 
 • Screening Period: Up to 4 weeks • Treatment Period: Study subjects will receive monotherapy of SCB01A until disease progression, intolerable toxicity, consent withdrawal, or death, whichever occurs first. • Follow-Up Phase: 27 weeks (± allowed windows) 
Total Study Duration: Around 52 weeks
	

Inclusion Criteria: Subjects are required to meet all of the following criteria for enrollment into the study.
 
 1. Aged ≥20 years; 2. Signed informed consent obtained prior to initiation of any study-specific procedures and treatment; 3. Histological or cytological confirmed squamous cell carcinoma of head and neck, excluding nasopharyngeal carcinoma; 4. Subjects with unresectable, unfeasible radiotherapy, recurrent or metastatic head and neck squamous cell carcinoma, after previous treatment with platinum agent; 	

Name of Sponsor/Company: SynCore Biotechnology Co. Ltd.	
Name of Study Product: SCB01A	
Protocol Number: SCB01A-22	Indication: Recurrent or metastatic squamous cell carcinoma of head and neck

5. Subjects must have at least one measurable tumor lesion as defined by RECIST version 1.1 as assessed by the investigator (local radiological image assessment) or clinically evaluable disease. Physical and neurological examinations, and radiographic studies have to be performed within 28 days of Cycle 1 Day 1;
 
6. Eastern Cooperative Oncology Group (ECOG) Performance Status (PS) 0-1;
 
7. Life expectancy of 12 weeks or longer;
 
8. Concurrent local therapy is not allowed, but concurrent palliative radiation therapy to non-measurable sites of disease such as painful bone metastasis is permitted;
 
9. All eligible subjects of childbearing potential have to use effective contraception; that is, double barrier contraceptive methods;
 
10. Documented progressive disease within past 6 months;
 
11. Adequate bone marrow reserve, cardiac, renal and liver function:
 
 Absolute neutrophil count (ANC) $> 1.5 \times 10^9/L$; White blood cell (WBC) $> 3 \times 10^9/L$; Platelet count $> 75 \times 10^9/L$; Hemoglobin $> 9 \text{ g/dL}$ ($> 5.6 \text{ mmol/l}$); Prothrombin time (PT)/international normalized ratio (INR) $\leq 1.5 \times$ upper limit of normal (ULN); Creatinine clearance (Cockcroft & Gault formula) $> 50 \text{ mL/min}$; Alanine aminotransferase (ALT, SGPT) and aspartate aminotransferase (AST, SGOT) and Alkaline Phosphatase (ALP) $< 3 \times$ ULN; $AST/ALT \leq 5 \times$ ULN if liver metastasis; Serum albumin $\geq 3 \text{ g/dL}$; Total Bilirubin $\leq 1.5 \times$ ULN; QTc $< 450 \text{ msec}$ 	

Exclusion Criteria: Subjects meeting any of the following criteria will be excluded from the study.
 
 Known primary CNS malignancy or CNS involvement (except for brain metastases that have been treated and are stable and subject is off steroids); Chemotherapy, radiation therapy, major surgery or investigational agents including immune or target therapies less than 4 weeks prior to study drug treatment; History of malignancy other than head and neck cancer with the exception of early stage non-melanoma skin cancer or carcinoma in situ of cervix; History of liver cirrhosis; Active hepatitis B or hepatitis C infection; Clinical significant pulmonary obstructive or clinical significant pulmonary restrictive diseases (grade > 2); Clinically significant cardiac disease (NYHA class > 2); Other serious illness or medial conditions, such as active infection, unresolved bowel 	

Name of Sponsor/Company: SynCore Biotechnology Co. Ltd.	
Name of Study Product: SCB01A	
Protocol Number: SCB01A-22	Indication: Recurrent or metastatic squamous cell carcinoma of head and neck

obstruction, or psychiatric disorders;
 
9. Known HIV positivity;
 
10. Pregnant or breast-feeding subjects, and men and women of child-bearing potential not using effective contraception while on study treatment;
 
11. Known hypersensitivity to any component of SCB01A or excipients including Solutol[®], alcohol, and PEG300;
 
12. History of exposure to SCB01A or its analogues;
 
13. History of active or significant neurological disorder or psychiatric disorder that would prohibit the understanding and giving of informed consent, or would interfere with the clinical and radiological evaluation of central nervous system during the trial;
 
14. Peripheral neuropathy (\geq grade 2);
 
15. Any other reason the investigator deems the subject to be unsuitable for the study.
	

Endpoints:
 
Primary endpoint:
 
 Objective response rate (ORR), defined as complete response (CR) + partial response (PR), according to RECIST v1.1 criteria 
Secondary endpoints:
 
 Progression free survival (PFS) Overall survival (OS) after first treatment with SCB01A Best overall tumor response after treatment with SCB01A Safety: The safety endpoints used to achieve the secondary objectives of this study are: 
 Hematology, clinical chemistry, coagulation factors and urinalysis laboratory data changes AE/SAE incidence Physical examination result changes Vital sign changes Electrocardiogram (ECG) (including PR, QRS, QTc intervals) results 
PK: Maximum plasma concentration [C_{max}], clearance [CL], volume of distribution [Vd], half-life [$t_{1/2}$], elimination constant [K_{el}], mean residence time [MRT] and time to maximum concentration [T_{max}])
	

Criteria for Evaluation:
 
Efficacy measurements:
 
Tumor Measurement: Tumor response will be assessed by using computerized tomography (CT) or MRI scans according to RECIST v1.1 at baseline, end of the first 3 cycles, and every three cycles thereafter until progression of disease. For subjects who meet objective response criteria after the first 3 cycles of study treatment, confirmative radiological tumor assessments will be performed at least 4 weeks later.
	

Name of Sponsor/Company: SynCore Biotechnology Co. Ltd.	
Name of Study Product: SCB01A	
Protocol Number: SCB01A-22	Indication: Recurrent or metastatic squamous cell carcinoma of head and neck
Scans must include brain, chest, abdomen, and pelvis. The imaging technique used at baseline should be used throughout the study.	

 • ORR is defined as the percentage of subjects who have achieved confirmed CR and PR during treatment phase, according to RECIST v1.1. Not-confirmed CR or PR, or withdraw for DLT are counted as non-responder. • PFS is defined as the time from the start of treatment up to the date of first progression based on RECIST v1.1 or the date of death, whichever comes first. • OS is defined as the time from the start of treatment up to the time that the subject is still alive. • Best overall tumor response defined as the best response from start of treatment through all treatment phase or until disease progression/recurrence. 
Survival data will be collected throughout the active treatment phase and during the 27 weeks follow-up period. Survival follow-up after subject discontinuation of treatment will be conducted every 3 weeks during the first 9 weeks, thereafter every 9 weeks until the end of the study to assess for survival. Survival rate will only be assessed in subjects with measurable disease at baseline.
 
Dose Limiting Toxicity (DLT):
 
All toxicities will be classified according to the National Cancer Institute (NCI) Common Terminology Criteria for AEs (CTCAE) version 4.03. DLT will be defined as the occurrence of any of the following criteria unless there is definitive alternative evidence that administration of SCB01A did not cause the specific toxicity:
 
 • Grade 4 neutropenia exceeding 5 days' duration; • Grade 4 thrombocytopenia; • Grade 4 anemia; • Grade 3 or greater neutropenia with complications (e.g., fever, infection etc.); • Grade 3 or greater thrombocytopenia with complications (e.g., bleeding); • Grade 3 or greater non-hematological AEs including Grade 3 unmanageable nausea and vomiting that persist for 3 or more days after drug administration. Grade 3 fatigue lasting for ≤ 1 week is not considered as a DLT; • Grade 3 or greater prolonged QTc interval; • Grade 3 or greater neurotoxicity; • Delayed treatment exceeding 14 days duration due to drug-related toxicity; • Not able to recover from grade 2 neurotoxicity exceeding 3 weeks. 
Safety measurements:
 
The following safety assessments will be done during the study:
	

Name of Sponsor/Company: SynCore Biotechnology Co. Ltd.	
Name of Study Product: SCB01A	
Protocol Number: SCB01A-22	Indication: Recurrent or metastatic squamous cell carcinoma of head and neck

 • Incidence and intensity of AEs evaluated using the CTCAE version 4.03 • Incidence and intensity of clinically significant abnormal laboratory values evaluated using the CTCAE version 4.03 • Percentage of subjects experiencing dose modifications including delays or omissions or discontinuation of study medication • Physical examination findings • Neurological examination findings • Vital signs measurements • ECG (including PR, QRS, QTc intervals) findings • Nerve conduction velocity examination (baseline for all subjects; symptom occurring and end of the study for subjects with grade 2 or greater neurological symptom) 
PK measurements:
 
PK will be performed on subjects enrolled in stage I.
 
 • PK blood samples will be taken immediately pre-infusion then at 24, 25, 26, 28, and 32 hours after the start of infusion on Days 1 and 8 of Cycle 3 if dose level of Cycle 3 is 24 mg/m² (time window at each sample collected: ±5 min). 	
Statistical Considerations:	
Populations for Analysis	
Study subjects will be categorized into the following populations for analysis:	

 • Intention-to-treat (ITT) population: The ITT population consists of all subjects enrolled in the study and received at least one study treatment. • Per-protocol (PP) population: The PP population will consist of all subjects who (1) withdraw from study for DLT, or (2) completed at least 3 cycles of study treatment regimen, have measurable baseline disease and, at least, one post-baseline RECIST assessment (PD, SD, PR or CR). Subjects with a major protocol deviation or AE, deemed by the Medical Monitor to have an impact on the study endpoints, will be excluded from the PP population. • PK population: The PK population will consist of all subjects in stage I who received, at least, one dose of 24 mg/m² of SCB01A with sufficient post-dose bio-samples collected for PK profile characterization. 
Details of any other populations for analysis will be described in the statistical analysis plan (SAP).
	
Statistical Analysis	
Assumption of sample size calculation:	

 • Study design: Simon's two stage design • Type I error (one-sided): 5% • Power: 80% 	

Name of Sponsor/Company: SynCore Biotechnology Co. Ltd.	
Name of Study Product: SCB01A	
Protocol Number: SCB01A-22	Indication: Recurrent or metastatic squamous cell carcinoma of head and neck

 • Response probability of null hypothesis (P0): 0.05 • Response probability of SCB01A (P1): 0.20 
According to these hypotheses, up to 37 subjects need to be recruited into the study (including 10 evaluable subjects in the Stage I and 19 evaluable subjects in Stage II, with the additional 8 subjects to account for replacement of subjects those who withdraw, i.e. dropout rate is 20%). At least 4 subjects are required to achieve CR or PR after treatment with SCB01A for the study to meet its primary objective. The trial will be discontinued if no objective response is observed after the Stage I tumor assessment review.
 
Stopping rule: stopped early for futility if less than 1/10 evaluable subjects showed ORR in Stage I; with no further investigation of the drug is less than 4/29 evaluable subjects achieve ORR by the end of Stage II.
 
Both according to ITT and PP approaches will be included in the efficacy analyses. The efficacy conclusion will be summarized according to analyses of PP population. Safety analysis will be done on ITT population. Inferential analysis results will be expressed as point estimates and their 95% confidence intervals (CIs). Analyses will be carried out using SAS[®] Software, version 9.4 or higher (SAS Institute, Cary, North Carolina, USA).
 
All time-to-event endpoints, including OS and PFS, will be reported in days (median with 95% CI and range) and calculated using Kaplan-Meier methods. Subjects who have not progressed or who have not died at the time of the analysis will be censored at the last assessment date.
 
PK Evaluations
 
The blood samples will be assayed for SCB01A and PK parameters (maximum plasma concentration [C_{max}], clearance [CL], volume of distribution [V_d], half-life [$t_{1/2}$], elimination constant [K_{el}], mean residence time [MRT] and time to maximum concentration [T_{max}]) will be determined and presented graphically and descriptively (as appropriate).
 
A detailed SAP will be finalized prior to final database lock. Any significant changes to the analyses described in this protocol will be addressed in the SAP and the Clinical Study Report.
	
Duration of the Study	
The planned duration of the entire study is approximately 26 months with an enrollment period of 12 months.	
End of Study	

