- b) Dose maintained: If clinical benefit observed at Dose 1 and without DLT, the dose level can be maintained until PD, intolerable toxicity, consent withdraw or death.
2. Dose 2 (18 mg/m²), will be administrated for one cycle and safety and clinical benefit observation will be performed prior to drug administration on Cycle 3 Day 1.
- a) Dose de-escalation: if any DLT experienced before Cycle 2 Day 8, the dose will be de-escalated to Dose 2a (15 mg/m²) for Cycle 2 Day 8. If first DLT during Cycle 2 is experienced after Cycle 2 Day 8, the dose will be de-escalated to Dose 2a (15 mg/m²) for Cycle 3. If no DLT is observed in Dose 2a, the subjects will receive the Dose 2a until PD, consent withdraw or death. Once more dose de-escalation (Dose 2b, 12 mg/m²) will be allowed if another DLT is observed in Dose 2a.
- b) Dose maintained: If clinical benefit observed at Dose 2 and without DLT, the Dose 2 can be continued until PD, intolerable toxicity, consent withdraw or death.
3. Dose 3 (24 mg/m²), will be administrated for one cycle and safety and tumor assessment will be performed prior to drug administration on Cycle 4 Day 1.
- a) Dose de-escalation: if any DLT experienced before Cycle 3 Day 8, the dose will be de-escalated to Dose 3a (20 mg/m²) for Cycle 3 Day 8. If first DLT during Cycle 3 is experienced after Cycle 3 Day 8, the dose will be de-escalated to Dose 3a (20 mg/m²) for Cycle 3. If no DLT is observed in Dose 3a, the subjects will receive the Dose 3a until PD, consent withdraw or death. Once more dose de-escalation (Dose 3b, 16 mg/m²) will be allowed if another DLT is observed in Dose 3a.

Figure 2: Dose Modification

If the subject experienced any neurotoxic DLT, the subject will be withdrawn.

Subjects will be considered to be non-evaluable for ORR if they receive study drug for fewer than 9 weeks (3 cycles) of treatment for any reason other than study-drug related toxicity. Non-evaluable subjects will be replaced.

All subjects will be treated until the occurrence of progressive disease, intolerable adverse events (AEs)/toxicity, consent withdrawal or death. After discontinuation of study treatment, all subjects will be followed for survival and disease-specific therapies of the clinician's choice will be administered. Follow-up visits will be scheduled every 3 weeks for 9 weeks (i.e. week 3, week 6, and week 9), thereafter every 9 weeks until the end of the study.

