3.3. End of Treatment (EOT) Evaluation/Early Withdrawal

EOT visit should be conducted 14 or 21 days (± 2 days) after last infusion, depending on last infusion was given on Day 8 or Day 1, respectively. Early withdrawal visit should be conducted after the subject receives the last dose of study treatment.

The following assessments will be performed at the EOT/early withdrawal visit:

- Physical examination
- Vital signs
- ECOG performance status
- AEs
- Concomitant medication
- 12-lead ECG
- Tumor assessment (radiological imaging)
- Laboratory tests (hematology, clinical chemistry and coagulation)
- Urinalysis

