6.1. Efficacy Measurements

Tumor response will be assessed by using computerized tomography (CT) or MRI scans according to RECIST v1.1 at baseline and at the end of Cycle 3 (at C3D21/EOT visit). For subjects who are continuing treatment beyond 3 cycles (9 weeks), tumor assessment will be performed at every three cycles until progression of disease (i.e. at or prior to Day 1 of Cycles 4, 7, 10 and so on). Any additional assessments can be arranged when clinically indicated.

Scans must include brain, chest, abdomen, and pelvis. The imaging technique used at baseline should be used throughout the study.

Subjects will be considered evaluable for tumor assessment in this study if they fulfill the criteria for evaluation according to RECIST v1.1, i.e., those subjects who undergo a baseline disease assessment within 4 weeks of treatment initiation, and who undergo at least 1 disease assessment on study (the following should be revised if revision in corresponding part in synopsis is accepted).

- ORR is defined as the percentage of subjects who have achieved confirmed CR and PR at a particular time point after first treatment, according to RECIST v1.1.
- PFS is defined as the time from the start of treatment up to the date of first progression based on RECIST v1.1 or the date of death, whichever comes first.
- OS is defined as the as the time from the start of treatment up to the time that the subject is still alive.
- Best overall tumor response defined as an objective response or stable disease of treatment phase.

Survival data will be collected throughout the active treatment phase and during the follow-up period. Survival follow-up after subject discontinuation of treatment will be conducted every 3 weeks during the first 9 weeks, thereafter every 9 weeks until the end of the study.

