8.2. Determination of Sample Size

Assumption of sample size calculation:

- Study design: Simon's optimal two stage design¹
- Type I error (one-sided): 5%
- Power: 80%
- Response probability of null hypothesis (P0): 0.05
- Response probability of SCB01A (P1): 0.20

According to these hypotheses, up to 37 subjects need to be recruited into the study (including 10 evaluable subjects in the Stage I and 19 evaluable subjects in Stage II, with the additional 8 subjects to account for replacement of subjects those who withdraw, i.e. dropout rate is 20%). At least 4 subjects are required to achieve CR or PR after treatment with SCB01A for the study to meet its primary objective. The trial will be discontinued if no objective response is observed after the Stage I tumor assessment review.

Stopping rule: The study will be stopped early for futility if less than 1/10 evaluable subjects showed ORR in Stage I; with no further investigation of the drug is less than 4/29 evaluable subjects achieve ORR by the end of Stage II.

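### The Simon decision rule drops and replaces patients who progress or die before three cycles, so the deciding response rate is biased upward

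*Protocol*

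**What the plan says.** **Decision population.** The synopsis (Statistical Considerations) plans efficacy analyses in both ITT and PP, then states: "The efficacy conclusion will be summarized according to analyses of PP population". SAP 9.7.1.2 repeats this. The synopsis (Trial Design) adds: "Per-protocol (PP) subjects will be considered to be evaluable for ORR conclusion; Non-evaluable subjects will be replaced". The planned enrolment is "10-13 subjects in Stage I and 19-24 subjects in Stage II, with replacement for those non-per protocol (non-PP) subjects".

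**Boundaries.** The synopsis and Protocol 8.2 stop for futility below 1/10 evaluable responders in Stage I, with "no further investigation of the drug is less than 4/29 evaluable subjects achieve ORR by the end of Stage II". Sections 8.5 and 8.7 repeat the fractions without the word evaluable.

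**Who counts.** The definitions differ:
- Synopsis and SAP 9.7.1.1: PP subjects are those who "withdraw from study for DLT, or (2) completed at least 3 cycles of study treatment regimen, have measurable baseline disease". A RECIST evaluation after baseline is also required. The Medical Monitor may exclude subjects for a major deviation or an AE.
- Protocol 8.3: the same three-cycle rule, without the DLT route into PP.
- Protocol 3.1: a subject is non-evaluable "if they receive study drug for fewer than 9 weeks (3 cycles) of treatment for any reason other than study-drug related toxicity".
- Protocol 6.1: evaluable for tumor assessment needs a baseline scan and covers subjects "who undergo at least 1 disease assessment on study", with no three-cycle rule.

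**SAP 9.8.** Five subjects were not evaluated because of clinical progression or AE/SAE. Such subjects are counted as non-responders and not as missing. The section does not say in which population.

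**The concern.** Treatment ends at progression, intolerable toxicity, consent withdrawal or death. A subject who progresses, deteriorates or dies in the first nine weeks, without a DLT or drug toxicity, cannot complete three cycles. That subject is non-evaluable, leaves the denominator and is replaced.

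A scan does not bring the subject back. Protocol 3.3 lists tumor imaging under "The following assessments will be performed at the EOT/early withdrawal visit", so progression may be documented on that scan, but PP still requires three completed cycles.

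These subjects are non-responders in practice. The first scheduled post-baseline scan is at the end of Cycle 3, and a response must be confirmed at least four weeks later. Entry to the decision set therefore depends on outcome, and in one direction. At stake are the Stage I gate, the final go/no-go decision, and what a positive result says about the patients who receive the drug.

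**Working it through.** **Inputs.** From the synopsis and Protocol 8.2: P0 = 0.05, P1 = 0.20, one-sided type I error 5%, power 80%, n1 = 10, n = 29, continue with at least 1 response, succeed with at least 4; dropout 20%, 8 extra subjects, cap of 37. From the synopsis (Planned Number of Subjects): upper stage limits of 13 and 24.

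**1. The plan's own design.** For response probability p,

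P(success) = Σ (x = 1 to 10) P[Bin(10, p) = x] × P[Bin(19, p) ≥ 4 − x].

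At p = 0.05:
- x = 1: 0.3151 × 0.0665 = 0.0210
- x = 2: 0.0746 × 0.2453 = 0.0183
- x = 3: 0.0105 × 0.6226 = 0.0065
- x ≥ 4: 0.0010

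The sum is 0.0468. At p = 0.20 the same formula gives 0.8011. A full search confirms 0/10 and 3/29 as the Simon optimal design for these inputs. Recruitment is 29/0.80 = 36.25, rounded up to 37. The design arithmetic is correct.

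**2. Effect of dropping failures.** Assume that P0 = 5% is the rate in all treated subjects, and that a share q of them are dropped and replaced, none of them responders. The null rate among evaluable subjects is then 0.05/(1 − q). The documents do not give q, so a range is shown. The chance of passing Stage I is 1 − (1 − p)^10.

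| q | Evaluable null rate | Pass Stage I | Type I error, always 29 evaluable | 37-subject cap | Stage caps 13 and 24 |
|---|---|---|---|---|---|
| 0 | 5.00% | 40.1% | 4.7% | – | – |
| 5% | 5.26% | 41.8% | 5.5% | 5.5% | 5.5% |
| 10% | 5.56% | 43.5% | 6.4% | 6.4% | 6.4% |
| 20% | 6.25% | 47.6% | 9.0% | 8.5% | 8.1% |
| 30% | 7.14% | 52.3% | 12.9% | 9.8% | 9.1% |

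The two capped columns average the rule over the number of evaluable subjects actually reached: min(29, Bin(37, 1 − q)) overall, or min(10, Bin(13, 1 − q)) and min(19, Bin(24, 1 − q)) by stage. At q = 30% the cap usually prevents 29 evaluable subjects, so 12.9% is an upper bound only.

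Type I error reaches 5% at an evaluable null rate of 0.0511, which is q = 1 − 0.05/0.0511 ≈ 2.1%. That is 0.021 × 37 ≈ 0.8 of a subject. It shows how little slack the design has; the excess at that q is trivial.

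**3. If SAP 9.8 puts non-evaluable subjects back in the denominator.** Suppose all treated subjects count and 4 responses still suffice. With the gate at 10, type I error runs from 5.1% (30 counted) to 8.6% (37 counted). With 13 in Stage I and 37 in all it is 9.7%, the upper case.

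**4. If P0 refers to evaluable subjects.** Type I error stays at 4.7%.

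**The case against.** The strongest reply is that both boundaries are written for evaluable subjects, so P0 and P1 are naturally evaluable-subject rates. Type I error and power are then as planned, and only generalisability is in question. That reading is possible and makes the inflation conditional. It does not remove the bias relative to treated patients, and the documents never state the denominator of P0.

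The size of q can also be challenged. Progression at the scheduled end-of-Cycle-3 scan stays in PP. DLT withdrawals stay as non-responders under the synopsis and SAP. Eligibility requires ECOG 0–1 and a life expectancy of at least 12 weeks. The 20% covers all withdrawals, so it is the upper case for the plan's own figure: if a quarter or a half of them are dropped failures, q is 5% or 10%. Subjects excluded for a major deviation need not be non-responders. All of this stands, and it argues for the lower rows of the range.

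SAP 9.8 and the planned ITT analysis are partial remedies. SAP 9.8 itself says such subjects tend to be treatment failures. But no decision rule is attached to ITT, and SAP 9.8 leaves the PP definition, the PP-based conclusion and the four-response requirement unchanged. The SAP text supplied is an extract that points to a fuller plan, which may name the population; the text available does not.

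The SAP is partly in the past tense, so a new threshold now could be a post hoc change. That limits the choice of fix. The wording in Protocol 6.1 concerns tumor assessment and carries an open drafting note, so it is weaker evidence of a rival denominator than the conflict among the synopsis, 3.1 and 8.3.

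**Conclusion.** The concern holds and must be fixed. The decision set excludes early failures because of their outcome, so the response rate it yields is biased upward for treated patients whatever P0 means.

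The excess type I error depends on two assumptions: that P0 = 5% is a treated-subject rate, and that dropped subjects are non-responders. Under them it is 5.5% to 6.4% for 5% to 10% dropped, and 8.1% to 9.0% at 20%, depending on how the caps bind. The Stage I gate loosens too, from 40.1% to 47.6% at 20%. A just-positive 4/29 = 13.8% would be 4/37 = 10.8% if eight subjects had been replaced.

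Separately, the definitions of evaluable and PP conflict, and SAP 9.8 does not say whether it changes the denominator of the 4/29 rule. The same data could therefore give different decisions.

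**What to change.** 1. State that P0 and P1 refer to treated subjects. Apply the 1/10 and 4/29 rules to the first 10 and first 29 treated, in order of first dose. Count early or clinical progression, death, withdrawal, DLT withdrawal and a missing post-baseline scan as non-response. Do not replace treated subjects. Keep PP as supportive.
2. Have SAP 9.8 name the population and denominator to which its rule applies.
3. Use one definition of evaluable and PP across the synopsis, Protocol 3.1, 6.1 and 8.3 and SAP 9.7.1.1. Remove the Medical Monitor's discretion to exclude subjects from the decision set for an AE.

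An alternative to the 29-subject rule is to count 37 treated (13 in Stage I, at least 1 response to continue) and require 5 responses: type I error 3.3%, power 85.8%. It changes the threshold and departs from the optimal design, so it is defensible only if set before responses are known. If replacement has already taken place, items 1 and 2 can still be done by ordering subjects by first dose and recording the change in the SAP and study report.

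**Cost.** The change is one of wording, since ITT efficacy is already planned. The reported response rate will be lower. If P1 = 20% holds in all treated subjects, power is 80.1% (29 treated) or 85.8% (37 treated, 5 responses). If it holds only in evaluable subjects, the treated rate is 0.20 × (1 − q). Power is then 73.0% or 78.8% with 10% early failures, and 64.0% or 69.2% with 20%. Restoring 80% would need more subjects, and the plan should say so.
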